To generate evidence on what works to prevent mental illness among forcibly displaced adolescent girls, Washington University in St. Louis, Universidad de Los Andes, Women's Refugee Commission, and Mercy Corps are conducting a hybrid type 1 effectiveness-implementation pilot randomized-controlled trial (RCT) of Sibling Support for Adolescent Girls in Emergencies (SSAGE). SSAGE is a whole-family and gender-transformative mental health intervention that aims to foster more secure family attachments, improve girls' self-esteem, and strengthen healthy coping skills on the path to improved mental health for forcibly displaced adolescent girls. The objectives of this hybrid type 1 pilot RCT are twofold. First, the study aims to examine the preliminary effectiveness and mechanistic pathways of SSAGE to prevent mental health disorders among recently arrived, forcibly displaced adolescent girls in Colombia; and second, the study seeks to assess the feasibility, acceptability and fidelity of the SSAGE intervention and identify determinants of successful implementation.

Study objective

- Primary Objective: The study aims to assess the effectiveness of the SSAGE intervention in preventing mental health disorders among recently displaced adolescent girls in Colombia, particularly focusing on reducing symptoms of anxiety, depression, interpersonal sensitivity, and somatization.

- Secondary Objective: The study seeks to explore the mechanistic pathways through which SSAGE operates, including its impact on family attachment, gender equitable family functioning, self-esteem, and coping strategies.
- Implementation Evaluation: Additionally, the study will evaluate the feasibility, acceptability, and fidelity of implementing SSAGE, including identifying barriers and facilitators to successful implementation at endline.

Methodology

We will undertake a hybrid type 1 effectiveness-implementation pilot RCT to test the effectiveness and mediators of SSAGE while simultaneously using a concurrent, convergent mixed methods design to examine the acceptability, feasibility, and fidelity of the intervention.

Screening for Eligibility: Inclusion Criteria

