Recruitment for this study will draw from families who fled Venezuela and relocated to Colombia within the last year. Included among this population are families originally born in Colombia who had previously emigrated to Venezuela for at least five years and subsequently returned to Colombia. Eligibility requirements include adolescent girls aged 13-19 years old who: live with a male and female caregiver and an adolescent male sibling or relative; immigrated to Colombia within the last year; are available, along with their family members, to participate in the SSAGE intervention for three months; and are available to participate in survey questionnaires immediately before and one month after the intervention (please see Figure 1 for a study schedule). We will recruit 180 adolescent girls from 180 families. Study participants will be recruited by Mercy Corps and consented and enrolled in the study by Los Andes University.

Figure 1. Schedule of enrolment, interventions, and assessments

DATA ANALYSIS AND DISSEMINATION												
Analysis					X	X	X	X	X	X		
Write-up of findings									X	X	X	X
Dissemination											X	X

Subject Recruitment, enrollment, treatment assignment and sample size

Following confirmation of eligibility criteria, the study team will obtain informed parental consent and direct assent from potential adolescent girl participants. Every adolescent girl recruited to the study will be assigned a unique study identification number to enable tracking survey responses across points of data collection.

Sample size and power analysis: To detect a medium effect size in our primary outcomes of interest of $d=0.5$, assuming statistical power of 80% and a one-sided alpha of 0.05, we need a sample size of 63 adolescent girls in each study arm. We expect approximately 20% attrition from baseline to T2 either through: (1) declining to participate in subsequent rounds of data collection or (2) data collectors' inability to locate the participant. Additionally, when estimating the effect of SSAGE on the four outcomes of interest, we will exclude adolescent girls already exhibiting above-threshold scores on the four-dimension measure of mental health symptoms at baseline as it would not be possible to 'prevent' mental health disorders in this subgroup. We expect this to result in the loss of an additional 10% of the initial sample. As such, we require a sample size of 90 girls for each study arm.

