To prioritize participant safety, support services will be readily accessible to participants through Mercy Corps and other local resources if they experience any adverse events or discomfort during participation. Confidentiality measures will also be implemented to protect participant privacy and ensure the security of personal information. Participants will be reassured of their right to withdraw from the study at any time without facing any negative consequences.

Data Analysis

Statistical methods

To assess the effectiveness of SSAGE in preventing mental health disorders, we will test the null hypothesis that adolescent girls who participate in SSAGE exhibit the same or greater levels of mental health symptoms as compared to girls who receive care as usual. We will test this hypothesis using both an intent-to-treat and per protocol analytical approach (41,42). We will employ generalized linear regression models to estimate the effect of the intervention on the primary outcomes, controlling for covariates not balanced between the two study arms at

baseline; given that treatment assignment is random, we expect that we will not need to control for many covariates. Per protocol analysis will also be conducted, leveraging attendance data from all participating family members. The threshold for meeting program adherence will be defined alongside program implementers prior to program implementation.

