Title: Sibling-Support for Adolescent Girls (SSAGE): A study protocol for a pilot randomized-controlled trial of a whole-family, gender transformative approach to preventing mental illness among forcibly displaced adolescent girls

NCT number: NCT06078124

Date: July 20, 2024

Statistical Analysis Plan (SAP)

Study Title: Sibling-Support for Adolescent Girls (SSAGE): A study protocol for a pilot randomized-controlled trial of a whole-family, gender transformative approach to preventing mental illness among forcibly displaced adolescent girls

Study Type: Pilot Randomized Controlled Trial (RCT)

Version: July 2024

1. Objectives

- To assess the impact of the SSAGE intervention on adolescent girls' anxiety and depressive symptoms, self-esteem, family functioning, gender equitable household task sharing, and coping skills
- To estimate both the intent-to-treat (ITT) and the local average treatment effect (LATE) of the intervention using instrumental variable analysis.
- To explore the role of participant characteristics in loss to follow-up and outcome changes.

2a. Primary Outcomes

- DSM-V cross-cutting youth: Respondents will be asked to indicate the frequency of 19 symptoms in the previous two weeks, selecting from the following response options: 0- Never; 1- Rarely (1 or 2 days); 2- Slightly (between 3 and 6 days); 3- Moderately (more than 7 days of the last two weeks); and 4-Severely (Every day in the last two weeks). Respondents will also report whether they have engaged in each of five behaviors related to drug and alcohol use, self-harm and suicide ideation (answering yes or no) in the last two weeks and whether they have ever attempted suicide in their lifetime (yes or no). The included symptoms are meant to represent 12 domains of mental disorders: somatic symptoms, sleep problems, inattention, depression, anger, irritability, mania, anxiety, psychosis, repetitive thoughts and behaviors, substance use, and suicide ideation/attempts. A respondent will be flagged as requiring further inquiry for a given domain if they answer '2' or higher on at least one of the symptoms in each respective domain. As such, this outcome will be operationalized as 12 dichotomous variables reflecting the 12 domains.

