- Depression and anxiety symptomology: Will be measured using the Revised Children's Anxiety and Depression Scale (RCADS-25). The RCADS-25 asks respondents to indicate how frequently they have experienced each of 25 symptoms. Possible responses include 0- Never; 1-Sometimes; 2-Frequently; and 3-Always. An overall RCADS-25 score will be created by adding the responses across all 25 items and looking up the corresponding T-score from a previously created T-score chart based on gender and grade.

2b. Secondary Outcomes

- Family functioning: A modified version of the Family Attachment Changeability Index 8 (FACI-8) will be used to measure family functioning. This version includes 12 items (some are reverse scored) and asks respondents to indicate how common each item is on a 4-point likert scale from “never” to “always.” Scores may assume a value from 12 to 48, with higher scores signaling greater family functioning.
- Self-esteem: captured using the Rosenberg Self-Esteem Scale (RSES). The RSES asks respondents to indicate their level of agreement with ten statements on a 4-point likert scale ranging from “totally disagree” to “totally agree”. After reverse scoring five of the ten items, the final score represents the sum of all items. Scores may assume a value from 10 to 40 where higher values reflect greater self-esteem.
- Coping: A modified version of KidCOPE will be used to assess the use of 15 healthy and unhealth coping strategies in the last two weeks. For each coping strategy, respondents will be able to indicate how often the strategy was employed in the last two weeks using a 4-point likert scale ranging from “never” to “almost all of the time.” Each coping strategy will be examined separately.

3. Study Sample

Eligibility criteria included adolescent girls who had migrated from Venezuela or who were born in Colombia and had previously emigrated to Venezuela for at least five years and recently returned to Colombia. In order to minimize community tensions between migrant and host populations, a few adolescent girls from internally displaced or host families who met all other inclusion criteria were included in the study. Other eligibility criteria included being 13-19 years old, being available to participate, along with their family members, to participate in the SSAGE intervention for twelve weeks, and being available for endline data collection immediately following the completion of SSAGE.

4. Descriptive and Baseline Analysis

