5.1. Intent-to-Treat (ITT) Analysis

OLS regression models will estimate the average treatment effect of assignment to the treatment group on changes in each outcome.

Models:

1. Bivariate association between treatment assignment and outcome change.

2. Model 1 + controls for baseline value of outcome.
3. Model 2 + controls for baseline covariates associated with outcome of interest at baseline.

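### Thirteen primary variables, three models each, with no lead outcome, lead model, success rule or multiplicity control, and a power statement not derived for twelve of them

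*SAP*

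**What the plan says.** SAP 2a (Primary Outcomes) lists two instruments. For the DSM cross-cutting measure, "this outcome will be operationalized as 12 dichotomous variables reflecting the 12 domains". For the second, "An overall RCADS-25 score will be created by adding the responses across all 25 items", which is then converted to a T-score. That makes 12 binary variables and one continuous one.

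SAP 5.1 fits three OLS models to the change in each outcome. Model 1 is "Bivariate association between treatment assignment and outcome change". Model 2 is "Model 1 + controls for baseline value of outcome". Model 3 adds covariates associated with the outcome at baseline. None is named as the lead. The SAP states no alpha.

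The protocol (Statistical methods) sets a directional null: "we will test the null hypothesis that adolescent girls who participate in SSAGE exhibit the same or greater levels of mental health symptoms". Its sample size section has one calculation, at d = 0.5: "To detect a medium effect size in our primary outcomes of interest", "assuming statistical power of 80% and a one-sided alpha of 0.05". This gives 63 per arm. Losses of 20% to attrition and a further 10% to a baseline exclusion raise it to 90 enrolled per arm. The same section refers to four outcomes, which matches neither the protocol's Table 1 (two primary constructs) nor the SAP's 13 variables. The primary objective describes the trial as "particularly focusing on reducing symptoms of anxiety, depression, interpersonal sensitivity, and somatization".

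**The concern.** A confirmatory claim needs one stated route from data to conclusion. Here there are 13 primary variables and three models for each, and nothing says which result, or how many, would count as success. That choice could be made after the results are known. If any single significant benefit were taken as success, the error rate would be far above the nominal level.

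The power statement claims to cover the primary outcomes together, but d = 0.5 is a standardised difference in means. For a binary flag, power depends on the flag rate in the control arm, and neither document gives one. A null result on a domain flag would therefore be hard to interpret.

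**Working it through.** **1. The plan's own sample size.** Inputs from the protocol: d = 0.5, power 80%, alpha 0.05. The normal-approximation formula is n per arm = 2(z_alpha + z_0.80)²/d².

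- One-sided 0.05: 2(1.645 + 0.842)²/0.25 = 49.5, so 50 (51 by the t distribution).
- Two-sided 0.05: 2(1.960 + 0.842)²/0.25 = 62.8, so 63 (64 by the t distribution).

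The 63 is reproduced only as two-sided 0.05. The inflation is reproduced: 63/(1 − 0.30) = 90. With 63 per arm and d = 0.5, the noncentral t gives power of 87.4% at one-sided 0.05 and 79.5% at two-sided 0.05.

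**2. False positives across 13 variables, one model each.** If the tests are independent, the chance of at least one is 1 − 0.95^13 = 0.487. For two-sided tests counting only false benefit, it is 1 − 0.975^13 = 0.280. Symptom domains are likely to be positively correlated, so I also took 13 equicorrelated normal statistics. The correlations are assumptions, because the documents give none.

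| Test at 5% | Independent | 0.3 | 0.5 | 0.7 |
|---|---|---|---|---|
| One-sided (false benefit) | 49% | 36% | 28% | 21% |
| Two-sided, false benefit only | 28% | 21% | 17% | 12% |
| Two-sided, either direction | 49% | 42% | 33% | 24% |

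Free choice among three models can only raise these figures.

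**3. Power for a single flag.** The documents give no flag rates, so I assumed control-arm rates of 5% to 70%. First reading: d = 0.5 is a shift in an underlying symptom, so p2 = Φ(Φ⁻¹(p1) − 0.5). This takes 5% to 1.6%, 20% to 9.0%, 50% to 30.9% and 70% to 51.0%. The test is a pooled-variance comparison of two proportions at follow-up.

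| Analysed per arm | One-sided 0.05 | Two-sided 0.05 |
|---|---|---|
| 63 | 28–72% | 19–60% |
| 72 (90 less 20% attrition, no baseline exclusion) | 31–77% | 21–66% |
| 90 (all randomised) | 36–85% | 25–76% |

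At 90 per arm, one-sided power passes 80% for control rates of 40–70%. This model suits flags built on the 0–4 frequency items. I do not claim it for substance use or suicide ideation/attempts, which rest on yes/no items.

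Second reading: 0.5 is Cohen's h. Power at 63 per arm is then 85–88% one-sided and 76–80% two-sided for rates of 20–70%. This reading cannot cover the lowest rates: at 5%, 2·arcsin(√0.05) = 0.451, so a reduction of h = 0.5 is impossible.

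**4. Keeping all 13 primary.** Bonferroni gives 0.05/13 = 0.00385 per test. RCADS-25 power at d = 0.5 and 63 per arm falls to 54% one-sided or 45% two-sided. By the formula in step 1, restoring 80% would take 99 evaluable and 142 enrolled per arm one-sided, or 112 and 160 two-sided.

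**The case against.** Both documents call this a pilot, and the protocol's background speaks of preliminary effectiveness. Many statisticians would not ask for familywise control in such a trial. That softens the consequences. But the protocol also states a formal null, 80% power and a primary objective of assessing effectiveness, and the pilot label does not supply the missing decision rule.

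The 49% presumes that any one significant result would be called success, which the plan never says. That is fair: the missing rule is the defect, and the error rates show what an any-one-counts reading would cost. Independence is also the upper end of the range.

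SAP Objective 1 names anxiety and depressive symptoms and no other mental-health construct, which points towards RCADS-25. It is not a ranking, since 2a lists the DSM flags as primary too and depression and anxiety are among their domains. It does support the choice of lead outcome proposed here.

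The flag-power figures use a follow-up comparison of proportions, not the planned OLS on change with baseline adjustment, and the baseline exclusion would alter flag rates. Power under the planned analysis could be higher or lower. This stands, and the figures are illustrative only. What is secure is that no power was derived for the flags.

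**Conclusion.** The concern holds. The plan has 13 primary variables and three models for each, and no stated way to decide whether the trial succeeded. On an any-one-counts reading with one model per variable, the chance of a false benefit is 21–49% at one-sided 5% and 12–28% at two-sided 5%, for assumed correlations from 0.7 down to independence. Each figure is at least four times its nominal per-direction rate of 5% or 2.5%.

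The 80% power is not shown for 12 of the 13 primaries. Whether it falls short depends on flag rates, the number analysed and how 0.5 is read, none of which the documents settle.

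Separately, and without any assumption about flags, the stated one-sided alpha and the 63 per arm do not agree. This should be corrected before analysis.

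**What to change.** - Name the RCADS-25 T-score with SAP Model 2 (adjusted for baseline value) as the single primary analysis, with Models 1 and 3 as supporting. State that this replaces the covariate-imbalance rules in the protocol's Statistical methods and in SAP section 4 for the primary analysis.
- Make the 12 DSM domain flags secondary, with Holm or Benjamini-Hochberg adjustment across the 12.
- Limit the power statement to RCADS-25 and reconcile alpha and sidedness: 63 per arm gives about 80% at two-sided 0.05 and about 87% at one-sided 0.05. Remove the reference to four outcomes.
- Reword the protocol's primary objective to match. It also names interpersonal sensitivity, for which neither Table 1 nor the SAP lists a measure.

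This changes wording in both documents and needs no new data; 63 evaluable and 90 enrolled per arm can stand. The cost is that DSM domain results can no longer be claimed as primary findings. Somatization, which the primary objective names, loses its primary measure. A composite or a fixed testing order would also settle the question, but the choice must be written down before outcome data are seen by arm.

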- Baseline Balance: Descriptive statistics will be computed separately by study arm. Mean comparisons will be conducted using independent samples t-tests.
- Imbalance Adjustment: Outcomes found to differ significantly at baseline between groups will be included as controls in regression models of change scores.

5. Estimating Treatment Effects

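### Baseline adjustment follows a significance screen beside three unranked ITT models: name the baseline-adjusted model primary, drop the screen, and carry the baseline value into the IV analysis

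*SAP*

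**What the plan says.** Several places bear on baseline adjustment.

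- **SAP section 4, Imbalance Adjustment:** "Outcomes found to differ significantly at baseline between groups will be included as controls in regression models of change scores". The comparison is by t-test; no significance level is given.
- **Protocol, Data Analysis, Statistical methods:** the regression for the primary outcomes is run "controlling for covariates not balanced between the two study arms at" baseline. It gives no list of covariates and no criterion for imbalance.
- **SAP 5.1 (ITT):** three models of outcome change. Model 1 is "Bivariate association between treatment assignment and outcome change". Model 2 adds the baseline value of the outcome, with no test. Model 3 is "Model 2 + controls for baseline covariates associated with outcome of interest at baseline". None is named primary.
- **SAP 5.2 (IV):** two-stage least squares on outcome changes, with assignment as the instrument for adherence. No baseline control is mentioned.
- **SAP section 7:** a sensitivity comparison of change scores with endline models that control for baseline.

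The SAP does not say how the section 4 rule combines with Models 1 to 3 or with the IV model.

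**The concern.** Allocation is random, so any baseline difference between arms is chance. A p-value for that difference does not show whether adjustment will help. What counts is how strongly the baseline value predicts the endline value. A screen on significance omits a strongly prognostic baseline in most trials, and leaves a moderate imbalance uncorrected because it falls short of the threshold.

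The plan also contains the better analysis (Model 2) without giving it precedence. Three things are at stake:

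- Precision, if the unadjusted or screened change model becomes the headline.
- Error control, if whichever model is significant may be claimed.
- The IV estimate, for which section 4 is the only adjustment rule that could apply.

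**Working it through.** **The plan's own figure.** The Protocol's sample-size paragraph works from d = 0.5, "assuming statistical power of 80% and a one-sided alpha of 0.05", and concludes "we need a sample size of 63 adolescent girls in each study arm". With n = 2(z_alpha + z_beta)²/d² per arm:

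- One-sided 0.05: 2(1.645 + 0.842)²/0.25 = 49.5, so 50.
- Two-sided 0.05: 2(1.960 + 0.842)²/0.25 = 62.8, so 63.

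The stated 63 is therefore the two-sided figure, and I use two-sided 0.05 below. Inflation for 20% attrition and a further 10% baseline exclusion reproduces: 63/(1 - 0.30) = 90.

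**Inputs.** 63 evaluable per arm and d = 0.5 come from the Protocol. The baseline-endline correlation r is not in the documents; I assume 0.3, 0.5 and 0.7. Scores are taken as normal with SD 1 at both times.

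**Power by formula.** The residual SD is √(2(1 - r)) for an unadjusted change score and √(1 - r²) with baseline in the model. Power = Φ(0.5/(SD·√(2/63)) - 1.96), with √(2/63) = 0.178.

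| r | SD, change | Power | SD, adjusted | Power |
|---|---|---|---|---|
| 0.3 | 1.183 | 66.0% | 0.954 | 83.7% |
| 0.5 | 1.000 | 80.1% | 0.866 | 90.0% |
| 0.7 | 0.775 | 95.2% | 0.714 | 97.6% |

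At one-sided 0.05 the pairs are 76.6% and 90.3%, 87.7% and 94.5%, 97.6% and 98.9%.

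**Effect of the screen.** Simulation, 20,000 trials per setting, 63 per arm. The screened analysis adjusts only when the baseline t-test gives p < 0.05 (assumed level).

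| r | Unadjusted | Screened | Always adjusted | Type I error, screened |
|---|---|---|---|---|
| 0.3 | 65.1% | 66.3% | 82.7% | 3.9% |
| 0.5 | 79.4% | 80.3% | 89.3% | 4.4% |
| 0.7 | 95.0% | 95.2% | 97.3% | 4.6% |

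The screen recovers about one point or less of the 2 to 18 points available, because it triggers in only about 5% of trials. At 72 per arm (90 × 0.8, attrition only) the pattern is the same: screened against always adjusted is 72.6% and 87.7%, 85.7% and 92.7%, 97.4% and 98.7%.

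**Imbalance left in place.** At 63 per arm a baseline difference is non-significant up to 1.979 × 0.178 = 0.353 SD. Given a baseline difference D, an unadjusted change score is off by (1 - r)D in the opposite direction. At D = 0.353 that is 0.25, 0.18 and 0.11 SD for r = 0.3, 0.5 and 0.7, against a target effect of 0.5. With baseline in the model it is about zero.

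**Either model may be claimed.** Under no effect, counting a trial as positive if Model 1 or Model 2 reaches two-sided 0.05 gave 7.7%, 7.3% and 6.8% for r = 0.3, 0.5 and 0.7 (40,000 simulated trials each, 63 per arm). Model 3 is not counted.

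**IV model.** With one binary instrument and no covariates, the 2SLS estimate is the Model 1 difference divided by the between-arm difference in adherence. It inherits Model 1's imbalance, scaled up by that division.

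**Section 7.** Regressing change on arm plus baseline gives the same arm coefficient and standard error as regressing endline on arm plus baseline. The sensitivity comparison is thus an identity against Model 2, and informative only against a change model without the baseline value. It does not settle which model leads.

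**The case against.** The strongest answer is that the SAP already adjusts. Model 2 always includes the outcome's own baseline value, Model 3 builds on it, and section 7 adds endline models that do the same. A reader of section 4 alone might infer that baseline values enter only after a significance test. The documents do not support that: against Model 2 the power loss and the conditional bias are both zero. This part of the objection stands, and it confines the figures to Model 1, a screened change model, or the unadjusted IV model.

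Other points also stand:

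- A reader might infer that the screen inflates false positives. It does not; it is slightly conservative.
- A reader might infer that the unadjusted change score is biased. Over all randomisations it is unbiased; the shift above is conditional on an observed imbalance.
- The size depends on r. At 0.7 the loss is about 2 points.
- The calculations suit continuous scores such as the RCADS-25. They do not carry over directly to the 12 dichotomous DSM domains or the single coping items.
- Model 3 selects covariates by association with the outcome, not by imbalance between arms. That is a better criterion; its weakness is that the list is left to the data and can differ by outcome.

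What the objection does not answer is that nothing ranks the three models, section 4 remains a stated rule for the change-score models, and the IV analysis has no Model 2 to protect it.

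**Conclusion.** The point holds in a limited form. Both documents state an imbalance-driven adjustment rule that is inferior to fixed baseline adjustment. The SAP contains the better model but neither makes it primary nor reconciles it with section 4, and it leaves the IV model without a stated baseline control.

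If Model 1 or a screened change model is the headline, the cost at 63 per arm is about 16 to 18 points of power at r = 0.3, 9 to 10 at r = 0.5 and 2 at r = 0.7. This assumes continuous, roughly normal scores, d = 0.5 and two-sided 0.05. If Model 2 is the headline there is no loss. Leaving the choice open carries a type I error of about 6-8% if either Model 1 or Model 2 may be claimed. The direction of these results is secure; their size rests on an assumed correlation.

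**What to change.** - Delete the significance rule in SAP section 4 and the imbalance rule in the Protocol's Statistical methods. Keep the baseline table descriptive, without tests.
- In SAP 5.1 name Model 2 (arm plus the outcome's own baseline value) as the primary ITT model for every outcome, with Models 1 and 3 supportive.
- In SAP 5.2 include the same baseline value as an exogenous covariate, so that it enters both stages of the 2SLS model.
- If Model 3 is kept, replace its association screen with a short list of covariates fixed in advance on prognostic grounds.

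The cost is wording in two documents and one residual degree of freedom for the baseline value (124 to 123 with 126 girls), plus one for each extra term in Model 3. No further data or participants are needed.
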